2.2. Secondary Objectives

1. To determine whether the decision impact of the GC test is of benefit to patients. Specifically, is net benefit of GC use superior to those who do not have the GC test as assessed by decision curve analysis.
2. To determine whether use of the GC test results in decreased likelihood of adjuvant treatment for subjects with high CAPRA-S score (≥ 5) and increased adjuvant treatment for subjects with low CAPRA-S score (< 5). The hypothesis is that there is a non-zero interaction between GC test use and CAPRA-S.
3. To determine whether GC use is associated with earlier use of salvage therapies in CAPRA-S low risk patients and later use of salvage therapy in CAPRA-S high-risk patients.

4. To determine whether use of GC results in improved protection from BCR and metastatic progression.
5. To investigate the impact of GC use on QOL, and whether there is differential QOL impact among CAPRA-S high- and low-risk patients.
6. To determine whether collaborative-wide education and the use of CAPRA-S scores in the control group impacts rates of adjuvant radiotherapy compared to historical controls.

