Secondary Objective 3: Time-to salvage therapy initiation will be modeled using a Cox formulation of a Frailty regression model with a similar formulation (ie: main and random effects) to that used for the primary analysis. Kaplan-Meier curves for GC and UC arms will be plotted, as well as for combinations of high- and low-risk GC and CAPRA-S groups.

Secondary Objective 4: Time-to BCR and metastatic progression will be evaluated similarly to the model described for Secondary Objective 3.

Secondary Objective 5: Summary statistics for all QOL instruments and corresponding confidence intervals will be calculated and compared for the GC and UC subjects and shown graphically over time. Validated instruments are used to measure erectile function, urinary function, sexual interest, and sexual satisfaction. Scores for each domain will be scaled with a minimum to maximum range of 0-100. Comparisons between GC and UC subjects will be made at each timepoint (3, 6, 12 and 24 months after surgery) and on each domain and overall score (VAS 0-10), using an ANCOVA analysis including adjustment for time since surgery. Should the assumptions for ANCOVA not be met (strongly skewed data or substantial ceiling or floor effect) a semiparametric ANCOVA model will be used (as in Buja 1989) to adjust for time-from surgery. If the distribution of time-from surgery is similar in the two groups, a Mann-Whitney test for differences will be used to corroborate the ANCOVA model. For this secondary objective, there will be no adjustment for multiple comparisons across domains or time points.

Exploratory Objective: Using a variety of budget models the cost of care for patients in the GC vs. UC arms will be compared out to 3 years from surgery. This will include estimated costs for adjuvant therapy. Differences in total cost, and differential cost per patient (UC vs GC) will be calculated and compared using either standard t-tests if data is normally distributed or appropriate non-parametric test if data is right skewed.

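### Secondary Objective 5 asks whether the quality-of-life effect of GC use differs by CAPRA-S risk, but the planned QOL analysis compares the arms only overall and cannot answer that half

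*Combined protocol and SAP*

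**What the plan says.** Section 2.2, Secondary Objective 5, sets out to study the effect of GC use on QOL and, as a separate question, "whether there is differential QOL impact among CAPRA-S high- and low-risk patients".

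Section 7.3, Secondary Objective 5, gives the analysis: "Comparisons between GC and UC subjects will be made at each timepoint (3, 6, 12 and 24 months after surgery) and on each domain" as well as on an overall 0-10 score, "using an ANCOVA analysis including adjustment for time since surgery". If the ANCOVA assumptions fail, a semiparametric version is used. If time from surgery is similarly distributed in the two groups, a Mann-Whitney test corroborates the result. All three methods compare the arms as a whole. No multiplicity adjustment is made across domains or visits.

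Elsewhere the plan brings CAPRA-S in explicitly:

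- Objective 2 expects that "use of the GC test results in decreased likelihood of adjuvant treatment for subjects with high CAPRA-S score", with the reverse for low scores, and adds "The hypothesis is that there is a non-zero interaction between GC test use and CAPRA-S". Section 7.3 gives it a model with a CAPRA-S product term.
- Objective 3 borrows the primary model's effects and adds Kaplan-Meier curves by GC and CAPRA-S group. Objective 4 follows it.
- The descriptive risk categories in Section 7.1 (CAPRA-S 0-4 and 5 or more) are set up for treatment rates.

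**The concern.** The second half of Objective 5 is a question of effect modification: is the GC-UC difference in QOL the same in CAPRA-S high-risk and low-risk men? Answering it needs either a separate arm difference in each stratum or an interaction term, and the QOL analysis specifies neither. Because QOL has its own ANCOVA, it does not inherit the CAPRA-S terms written for Objectives 2 to 4, and correcting those models would not correct this one.

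Two things are at stake. Followed as written, the plan leaves half of a stated objective unanswered. If the gap is noticed only after the data are seen, the choice of cutpoint, domain and visit becomes post hoc, in a family of comparisons that already has no multiplicity control.

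A secondary worry is that an overall difference averages over the strata, so effects of opposite sign would partly offset one another.

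**Working it through.** The documents give no QOL effect size, SD or power, so there is no stated figure to reproduce.

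**1. Objective against analysis**

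| Part of Objective 5 | Analysis in Section 7.3 |
|---|---|
| Effect of GC use on QOL | Arm comparison by visit and domain, ANCOVA adjusted for time since surgery |
| Whether that effect differs by CAPRA-S risk | None |

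This establishes the gap without any arithmetic.

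**2. What the overall difference measures**

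Let the GC-UC difference be D_H in CAPRA-S high-risk men and D_L in low-risk men. The overall difference estimates p_H·D_H + p_L·D_L, while the objective asks about D_H − D_L. The first does not determine the second.

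Section 7.5.1 gives the mix. Paired so that each population sums to 100%, MUSIC is 55.8% low and 44.2% high, and PRO-ACT is 62.7% low and 37.3% high. If the effects had opposite signs, with the high-risk effect r times the low-risk effect in size, the share of the gross effect cancelled would be 1 − |p_H·r − p_L| / (p_H·r + p_L):

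| r | MUSIC mix | PRO-ACT mix |
|---|---|---|
| 0.25 | 33% | 26% |
| 0.5 | 57% | 46% |
| 1 | 88% | 75% |
| 2 | 77% | 91% |

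For r = 1 in MUSIC, the overall difference is 0.442d − 0.558d = −0.116d. Cancellation can be large or modest, and the documents do not fix r.

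**3. How large a stratum effect is plausible**

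Section 7.5 puts adjuvant treatment in CAPRA-S high-risk MUSIC patients at about 8%. If GC use removed all of it, the mean gain in that stratum through adjuvant treatment would be 0.08 × (points lost per treated man). On the 0-100 domain scale:

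- a gain of 2 points needs a loss of 2/0.08 = 25 points per treated man;
- a gain of 4 needs 4/0.08 = 50;
- a gain of 8 needs 8/0.08 = 100, the whole scale.

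Salvage treatment could add to this, but the documents give nothing with which to size it. Two points is used below.

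**4. Precision of the missing contrast**

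Assumptions: domain-score SD 25 (not in the documents), 1:1 allocation within strata, MUSIC mix, no clustering and no missing QOL data. N is 550 (Section 3) or 350 (Section 7.5.2).

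SE of the interaction = SD × sqrt(4/(N·p_H) + 4/(N·p_L)).

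- N = 550: 25 × sqrt(4/243.1 + 4/306.9) = 4.3 points, 95% half-width 1.96 × 4.29 = 8.4.
- N = 350: 25 × sqrt(4/154.7 + 4/195.3) = 5.4 points, 95% half-width 1.96 × 5.38 = 10.5.

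With stratum effects of +2 and −2 the contrast is 4 points. Two-sided power at 0.05 is Φ(4/SE − 1.96) + Φ(−4/SE − 1.96):

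- N = 550: 4/4.29 = 0.93, power about 15%.
- N = 350: 4/5.38 = 0.74, power about 12%.

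The overall comparison, with a true difference of 0.116 × 2 = 0.23 points and SE 25 × sqrt(4/550) = 2.1, has about 5% power.

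The SE is proportional to the SD. For SD 20 to 30 it is 3.4 to 5.2 points at N = 550 (power 21% to 12%) and 4.3 to 6.5 at N = 350 (power 15% to 10%).

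**The case against.** The strongest reply is that this is a narrow completeness gap. Objective 5 is secondary and investigative, with no QOL hypothesis or power claim. CAPRA-S is reported for every participant (Section 3.3) and the cut is already defined (Section 7.1), so stratum summaries can be added before analysis with no data lost. At realistic effect sizes both the overall and the interaction analysis would usually be inconclusive. All of this stands, and it limits the severity. It does not supply the missing analysis.

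A reader might infer three stronger claims, which the documents do not support:

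- *The plan expects opposite QOL effects that largely cancel.* Objectives 2 and 3 predict opposite shifts in adjuvant treatment and in salvage timing. No section predicts a direction for QOL, so opposite QOL effects are an inference through treatment burden. Other text points elsewhere. The exploratory objective looks to avoided treatment in many patients, a net reduction. Section 1 reports that a high GC score raised treatment among clinically high-risk men and a low score reduced it among low-risk men, which is movement both ways rather than one sign per stratum.
- *An interaction test would have high power.* That needs stratum effects such as 8 points, which the roughly 8% treatment rate puts at the ceiling of the scale for adjuvant treatment alone.
- *The plan would declare that GC use has no QOL effect.* Section 7.3 provides summary statistics, confidence intervals and plots. It has no rule that turns a non-significant difference into a finding of no effect.

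**Conclusion.** The point holds in a limited form. The QOL analysis as written cannot answer whether the effect of GC use differs by CAPRA-S risk, and no other section fills the gap. This follows from the text and needs no assumption about cancellation or effect size.

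That the overall difference might also understate stratum effects is conditional: it requires QOL effects of opposite sign, and the extent depends on their relative size.

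The added contrast will be imprecise. The standard errors of about 4.3 and 5.4 points rest on the assumed SD of 25, and missing questionnaires would widen them. The effect of clustering on them is unknown, because the 23% ICC in Section 7.5.1 concerns treatment decisions and no QOL correlation is given. Severity is low to moderate, and the primary conclusion is not affected.

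**What to change.** In Section 7.3, Secondary Objective 5:

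1. Add CAPRA-S (0-4 versus 5 or more) and an arm-by-CAPRA-S term to the QOL model, together with the center and period effects of the primary model, which the present ANCOVA does not mention.
2. Report the interaction estimate, and the GC-UC difference within each CAPRA-S stratum, with 95% confidence intervals.
3. State that these are estimates rather than powered tests, and that the overall difference alone does not address the second half of the objective.

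The cost is a short SAP amendment and a few model terms, with no new data. The downside is more secondary estimates with wide intervals. Four named domains plus the overall score at four visits give 5 × 4 = 20 interactions. If each were tested at an unadjusted 0.05, about 20 × 0.05 = 1 false positive would be expected under the null. That is a further reason to report intervals and not to pick out individual p-values.

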2.3. Exploratory Objective

1. To determine whether it is possible that use of GC will result in an overall reduced net cost to the healthcare system by avoiding treatment in many patients.

3. Study Design

This is a 4-5 year (up to 2 years enrollment , 3-year follow-up) prospective, cluster-crossover, unblinded, study of 550 subjects from at least fourteen centers of the Michigan Urological Surgery Improvement Collaborative (MUSIC), a physician-led quality improvement consortium comprised of the vast majority of urology practices within the state of Michigan.

According to the cluster-crossover design, each participating MUSIC clinical center within MUSIC will be randomized to either a Genomic Classifier care-based (GC) or Usual-Care-based (UC) strategy for a period of 3 months, during which all enrolled subjects within the center will be provided the assigned strategy. Random assignments will be generated centrally by a study statistician and provided to centers immediately before commencing enrollment in each 3-month period. The randomization will be based on a random block size of either 2 or 4. This will ensure that each center will have two periods of GC and two periods of UC during the enrollment period, maintaining study-wide balance and blinding of assignments in subsequent periods.

If enrolled during the GC period, both subjects and their treating physician will be provided GC (from GenomeDx) and CAPRA-S (from MUSIC-Central) to inform their treatment plan. In the UC periods, only the CAPRA-S results, provided by MUSIC-Central, will be available. Blinding of subjects and treating physicians will not be possible given the nature of the information.

Subjects enrolled to the GC arm will receive MUSIC-led education about the GC test. The pros and cons of the GC test need to be described by an unbiased clinician scientist including the past history of the test (published studies).

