7.5.1 Power and Sample Size Simulation

Generating CAPRA-S and GC Scores

Simulation was used to determine the sample size necessary to have adequate power to reject the null hypothesis, $H_0: \beta_2 = 0$, based on the model in Section 7.1. CAPRA-S and GC risk scores for the simulated datasets were based on the distributions observed in the PRO-ACT clinical utility study (Michalopolous 2014). The distribution of CAPRA-S risk in PRO-ACT clinical is similar to that of MUSIC (62.7% vs 55.8% low risk and 44.2% vs 37.3% high risk). The distribution of GC risk scores among MUSIC patients is unknown, but due to the similarity in CAPRA-S scores, it is assumed that it will also be somewhat similar to PRO-ACT.

To ensure a) the GC score distribution is comparable to PRO-ACT, b) the CAPRA-S risk distribution is as similar as possible to MUSIC, c) the true variability of the continuous GC score, and d) the underlying correlation between GC and CAPRA-S risk is maintained, the following procedure was used to generate GC and CAPRA-S scores for each simulated individual:

1. A random percentile is generated (0-100%) and rounded to the nearest 5%.
2. PRO-ACT scores with GC score (and corresponding CAPRA-S score) within that percentile range (eg: 20-25th percentile) are then selected.
3. A GC score is then generated as a uniform a random number between the maximum and minimum of the selected PRO-ACT GC scores.
4. An initial CAPRA-S score is then randomly sampled from the selected CAPRA-S scores. The initial CAPRA-S score is then incremented by 1-point (to a maximum of 12) with 75% probability to up-adjust the slightly lower risk in PRO-ACT.

Generating Enrollments

Based on data available from MUSIC-central, the peak performing clinical centers exceeded 10 radical prostatectomy cases per month, with case-loads below 5 per month for the 4th and 5^h centers. Enrollments per site*month were generated using a Poisson process using the following conservative means: Site 1: 10, Site 2: 10, Site 3: 5, Site 4: 5, Site 6-8: 4, Site 9 and higher: 2.

Sites were randomized to enroll subjects to the GC or UC arm for each period using a fixed-block size enrollment (2, 3, or 4 depending on the randomization ratio of the simulation). Period length varied from month to year.

Intra-Class Correlations

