In other clinical utility studies on GC (eg: Badani 2014) physicians reviewed several cases. With physicians as clusters, the ICC in this study is approximately 38% using methods of Wu (2012). In somewhat different scenarios, and with alternative methods of calculation Adams (2004) identified the IQR of ICCs as 3.5-28.4% in cluster-randomized trials. Assuming that the ICC for an entire clinical center will be less than for a single physician, and given the findings of Adams, an ICC of 23% was selected for the simulation – given the other parameter settings of the model, specified above, this is equivalent to setting $\rho^2 = 1$. A small intra-period (across sites) is also incorporated (ICC = 3%) to include the possibility of a temporal correlation across sites - potentially related to changes in educational materials or seasonal trends.

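### Arm sequences are blocked within each center but not linked across centers, so the GC:UC split within a calendar period is left to chance; volume-matched mirror sequences would remove most of that imbalance cheaply.

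*Combined protocol and SAP*

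**What the plan says.** Section 3 (Study Design) assigns each center to GC or UC for 3 months at a time. On the method it says "The randomization will be based on a random block size of either 2 or 4", and it concludes that "each center will have two periods of GC and two periods of UC during the enrollment period", with the further result quoted as "maintaining study-wide balance and blinding of assignments in subsequent periods". The list is drawn in one place: "Random assignments will be generated centrally by a study statistician and provided to centers immediately before commencing enrollment in each 3-month period". The trial is described as a "study of 550 subjects from at least fourteen centers".

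The power simulation (Section 7.5.1) is equally silent on any link between centers: "Sites were randomized to enroll subjects to the GC or UC arm for each period using a fixed-block size enrollment". It takes monthly enrolment means of "Site 1: 10, Site 2: 10, Site 3: 5, Site 4: 5, Site 6-8: 4, Site 9 and higher: 2"; site 5 is not listed. It also adds a small period ICC of 3% to allow for "temporal correlation across sites - potentially related to changes in educational materials or seasonal trends".

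Period enters the primary model as a random effect, and the group-by-period check as a fixed effect (Section 7.1). The models for Secondary Objectives 3 and 4 are said to have main and random effects similar to the primary model's (Section 7.3). For the QOL ANCOVA and Mann-Whitney test, the cost comparison and the Kaplan-Meier curves, Section 7.3 states no calendar-period term.

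**The concern.** Two GC and two UC periods per center balance the arms over that center's whole participation. They do not balance the arms across centers within a calendar quarter. When two centers supply about a third of the patients, a quarter in which both hold the same arm is lopsided.

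If practice, educational material or season shifts adjuvant use over time, arm becomes partly confounded with calendar period. A model with a period effect handles this but pays for it in precision. A comparison without one carries the shift as error in the arm difference, and ordinary standard errors do not show it. The plan allows for such shifts, while describing them as small.

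**Working it through.** **Inputs.** Monthly means from Section 7.5.1: 10, 10, 5, 5, [site 5 assumed 4], 4, 4, 4, then 2 for each of sites 9 to 14. Total: 20 + 10 + 16 + 12 = 58. N = 550 and 14 centers (Section 3). Site ICC 23% with variance 1, period ICC 3% (Section 7.5.1).

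**The plan's own figures.**
- If blocks of 2 or 4 are made to fill exactly four periods, every center gets 2 GC and 2 UC, as stated.
- Site ICC: 1/(1 + π²/3) = 23.3%, which matches 23%.
- Period variance: 0.133/(1 + 0.133 + 3.290) = 3.0%, so a 3% ICC corresponds to a logit variance of about 0.133.

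**Agreement of the two largest centers.** The possible sequences are four alternating-block ones with probability 5/24 each, and GC-GC-UC-UC and its mirror with probability 2/24 each. The chance that two independent centers draw the same sequence is (4×25 + 2×4)/576 = 18.75%. The chance of exact opposites is the same. Otherwise (62.5%) they agree in two of four periods. They therefore agree in half of periods on average, but in any one trial in 0, 2 or 4. When they agree, the expected split is (20 + 38/2)/58 = 67:33.

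**GC share in one period, independent sequences.** SD = 0.5·√Σw²/Σw. Σw² = 100 + 100 + 25 + 25 + 4×16 + 6×4 = 338, so SD = 0.5 × 18.38/58 = 15.9 points before enrolment noise. With site 5 at 5 per month it is 15.8.

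**With Poisson enrolment, 550 men over four full periods:**

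| | Independent | Mirror pairs |
|---|---|---|
| SD of period GC share | 16.3 points | 4.3 points |
| 95% range of period GC share | 19–81% | 41–59% |
| Schedules with a period beyond 70:30 | 58% | about 0% |
| Whole-trial GC share, 95% range | 46–54% | 46–54% |
| Arm information left after center and fixed period effects | 0.89 | 0.99 |
| Same, worst 5% of independent schedules | 0.75 or less | – |
| SD of calendar error with no period term, in period-effect SDs | 0.32 | 0.07 |
| Same, on the logit scale at period variance 0.133 | about 0.12 | 0.027 |

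**If enrolment stops at 550.** At the plan's rates this takes 550/58 = 9.5 months, early in the fourth period. The whole-trial GC share then ranges over 41–59% with independent sequences and 46–54% with pairs.

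**Arm effect in the random-period model.** In simulated null trials with about 8% treated, the SD of the arm log-odds ratio was 0.385 (independent) against 0.374 (paired). The variance ratio is (0.385/0.374)² = 1.06. With 11,852 trials, if split equally, Monte Carlo error puts the excess between about 1% and 11%. A linearised calculation with a GC-slope term in the model found the SE of the arm term lower by about 1% or less.

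**Primary slope.** Under assumed score distributions and a 9.5% event rate, power for β₂ was 91.5% (independent) and 91.6% (paired) at N = 550, and 77.0% and 76.6% at N = 350. There is no gain.

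**The case against.** A reader might infer that the plan's balance claim is false. The documents do not support that. The phrase follows directly from the two-plus-two rule and most naturally means balance over the whole trial, which the rule delivers when four full periods run. Nothing promises balance within a quarter, and Section 7.5.2 concedes that the ratio will not be exactly 1:1.

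A reader might also infer that centers are definitely randomized independently. That is read from silence; one statistician draws all the sequences and could already link them.

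Nor is the primary analysis at risk. It tests a slope within the GC arm in a model that contains period. The Secondary Objective 2 test (β₄) is likewise a slope among GC-arm subjects, so no clear gain should be claimed for it. In the simulated null trials type I error was about 4.6% under both designs, so the random-period model shows no inferential harm.

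Pairing is not free. It needs calendar-aligned starts, which the plan does not state, an even number of centers, reasonably stable volumes and retention of both partners.

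All of this stands, and it limits the point to precision and calendar error in arm contrasts. It does not remove it. A period term in the unadjusted comparisons would deal with the calendar error, but it would not recover the information lost to imbalance.

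**Conclusion.** This is a worthwhile low-cost improvement, not a defect in the primary analysis. With independent sequences, imbalance within calendar periods would be large: SD about 16 points, and about 58% of schedules with a period beyond 70:30. The price for GC-versus-UC contrasts is modest. Variance is about 6% higher with random periods (0.06 × 550 = 33 men), and about 10% of information is lost with fixed periods (0.10 × 550 = 55 men). These equivalents are best read as an upper range, for arm contrasts only.

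Comparisons with no period term carry calendar error with SD about 0.32 of a period-effect SD, against 0.07 under pairing. For QOL and cost the absolute size is unknown, because the plan gives no period variance for those outcomes.

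The figures assume independent draws, site 5 at 4 per month, 14 centers starting together, four periods with exact two-plus-two sequences, and period variance 0.133.

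**What to change.** In Section 3, state how sequences are generated across centers. For centers on the same calendar schedule:

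- Pair them by expected volume (1 with 2, 3 with 4, and so on).
- Draw one 2-GC/2-UC sequence per pair, and assign it and its mirror image at random within the pair.
- Keep the pairings undisclosed, and keep central release just before each period.
- Leave an odd or late-starting center on its own sequence.

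As a complement, add a calendar-period term to the QOL and cost comparisons in Section 7.3, and read the Kaplan-Meier curves alongside the period-adjusted frailty model.

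**Cost.** The central list changes; no patients, visits or data are added. Balance is partly lost if a partner withdraws or starts late. With aligned starts, pairing adds no predictability: the best guess of a center's next assignment is right 83%, 58% and 100% of the time for periods 2, 3 and 4 in both designs. With staggered starts, a partner's assignments could reveal later ones, which is why late starters should stay unpaired.
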